### **Specific Aims**

1. To determine whether 4 weeks of freeze dried strawberry consumption improves the lipid profile (primarily LDL-C, as well as total cholesterol, HDL-C, and triglycerides) and other CVD risk factors (i.e., glucose, insulin, and inflammatory markers).
2. To determine whether 4 weeks of freeze dried strawberry consumption improves vascular function, in terms of resting brachial and central blood pressure and arterial stiffness indices (i.e., augmentation index and pulse wave velocity).
3. To identify changes in the composition of the gut microbiome following 4 weeks of freeze dried strawberry consumption.

4. To determine whether there is a dose-response effect with greater improvements achieved following high dose (40 g/d) supplementation.

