### ***Statistical Analysis***

Statistical analyses for blood markers of CVD risk, markers of inflammation, and vascular function measurements will be performed using SAS (version 9.4; SAS Institute). Treatment comparisons will be made between each of the supplementation periods. The mixed models procedure (PROC MIXED) will be used to test the effects of supplementation, period, and their interaction on outcome measures. Selection of model covariance structures will be based on optimizing fit statistics (evaluated as lowest Bayesian Information Criterion). Mixed models for endpoint means and change scores will be evaluated. Change scores will be calculated by subtracting baseline values from endpoint values. Means will be reported as least-squares means  $\pm$  SEM. Baseline values will be included as covariates. For all tests,  $\alpha$  will be set at 0.05.

For gut microbiome analyses, microbial DNA sequences will be quality filtered at an expected error of less than 0.5% using USEARCH v7. After quality filtering, reads will be analyzed using QIIME 1.9.0. An Operational Taxonomic Unit (OTU) table will then undergo cumulative sum scaling (CSS) normalization prior to beta diversity and alpha diversity analyses. Principal coordinates analysis (PCoA) plots and ANOSIM tests for significance will be performed using a weighted unifracs distance matrix. Linear Discriminant Analysis (LDA) effect size (LEfSe) will be used to identify potential differences in the microbial community following each intervention. Exploratory Spearman rank correlations will be performed between bacterial taxa and other physiological measurements (e.g., LDL-C, blood pressure, and inflammatory markers) to identify potential microbial signatures associated with CVD risk reduction.

The Principal investigator, Co-Principal Investigator and Authorizing Official for the University of Arizona, have reviewed and approved the proposal for consideration of funding.

  
[name] 7/17/17  
Date

  
[name] 7/17/17  
Date

 for [name], Senior VP for Research 7/26/17  
Authorizing Official for the University of Arizona Date

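### No false discovery control is specified for the taxon-level LEfSe tests or the taxa-by-marker correlations, and the unit of analysis for the correlations is left open

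*Combined protocol and SAP*

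**What the plan says.** All of the relevant text is in the Statistical Analysis section of the combined protocol and SAP.

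- The first paragraph covers the non-microbiome endpoints: "Statistical analyses for blood markers of CVD risk, markers of inflammation, and vascular function measurements will be performed using SAS". Its last sentence gives an alpha for all tests, which "will be set at 0.05".
- The second paragraph covers the microbiome. After alpha diversity, beta diversity, PCoA plots and ANOSIM, it states: "Linear Discriminant Analysis (LDA) effect size (LEfSe) will be used to identify potential differences in the microbial community following each intervention". It gives no significance level, LDA cut-off, taxonomic level or prevalence filter.
- The correlations come last: "Exploratory Spearman rank correlations will be performed between bacterial taxa and other physiological measurements". The markers are an open list ("e.g., LDL-C, blood pressure, and inflammatory markers"), and the purpose is "to identify potential microbial signatures associated with CVD risk reduction".

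Under Specific Aims, a change in gut microbiome composition is the numbered Aim 3. The Gut microbiome analysis section has stool collected at baseline and after each supplementation period, so a participant gives up to four samples. Neither section mentions a false discovery rate, q-values, Bonferroni or any other adjustment, and nor does the rest of the document.

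**The concern.** LEfSe is the only planned analysis that names which taxa changed, and it is not labelled exploratory. It tests many taxa at once. With no error control, the resulting list mixes real and chance findings in unknown proportion, yet it would be read as part of the answer to a numbered aim.

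The correlations raise the same issue on a larger scale, because every taxon is crossed with every marker. They have a second gap. Their purpose concerns risk reduction, which is a change within a person, but the sentence relates taxa to measurements and does not say which visits are used. Change scores are defined only for the SAS endpoints. Correlating levels instead of changes would mostly describe how people differ from one another. Stacking a person's visits as if they were independent would also raise the error rate of every single test.

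**Working it through.** The plan states no number of tests and no expected error count, so there is no figure of its own to reproduce.

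**Inputs**

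- Per-test alpha: 0.05 (Statistical Analysis, read literally as covering all tests; two-sided assumed).
- Named markers: LDL-C, blood pressure and inflammation. The section on blood markers of inflammation lists only hs-CRP, so this is 3 markers, or 4 if systolic and diastolic pressure are counted separately.
- All measured markers (Specific Aims 1 and 2, plus hs-CRP): LDL-C, total cholesterol, HDL-C, triglycerides, glucose and insulin (6); hs-CRP (1); brachial systolic and diastolic, central systolic and diastolic, augmentation index and pulse wave velocity (6). Total 6 + 1 + 6 = 13.
- Participants: 40 expected completers (Summary).
- Number of taxa: not stated. **Assumption:** 100, with a range of 20 to 300.

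**Step 1. Taxon tests.** Expected false taxa under the global null = taxa × 0.05.

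- 100 × 0.05 = 5 for one pass; 20 taxa give 1 and 300 give 15.
- If all three pairwise powder comparisons were run: 100 × 3 × 0.05 = 15 (range 3 to 45).
- These counts are before any LDA effect-size cut-off, which could lower them.

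**Step 2. Correlations.** Expected false results = taxa × markers × 0.05.

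| Taxa (assumed) | 3 markers | 4 markers | 7 markers | 13 markers |
|---|---|---|---|---|
| 20 | 3 | 4 | 7 | 13 |
| 100 | 15 | 20 | 35 | 65 |
| 300 | 45 | 60 | 105 | 195 |

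Even the smallest cell, 20 × 3 = 60 tests, gives a chance of at least one false result of 1 − 0.95^60 = 0.954 if the tests are independent.

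Correlation among taxa or markers leaves the expected count unchanged and widens its spread. In 1,000 null simulations with n = 40, 100 taxa and 4 markers, the 5th to 95th percentile was 13 to 28 with independence and 8 to 42 with correlation 0.3 within taxa and within markers.

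**Step 3. Effect of adjustment.** The same simulations, for 50 to 100 taxa and 4 to 13 markers, were repeated with Benjamini-Hochberg at q = 0.05 over the whole taxa-by-marker family. The mean number of false findings fell to about 0.05 to 0.10 per study, and the chance of any was about 4% to 8%.

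**Step 4. Unit of analysis.** Suppose the four visits of each person are stacked, and taxon and marker are unrelated but each has within-person correlation ρ. The variance of the correlation coefficient is then inflated by about 1 + 3ρ², so a nominal 5% test rejects when |Z| > 1.96/√(1 + 3ρ²).

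| ρ | 1 + 3ρ² | Effective cut-off | Approximate type I error | Simulated (40 people × 4 visits) |
|---|---|---|---|---|
| 0.5 | 1.75 | 1.48 | 14% | 12–13% |
| 0.7 | 2.47 | 1.25 | 21% | 21–22% |
| 0.85 | 3.17 | 1.10 | 27% | 25–27% |

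With one value per person the simulated error is about 5%. The values of ρ are assumptions.

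**The case against.** Several points on the other side are sound.

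- **Scope of the 0.05 sentence.** It ends the SAS paragraph, so applying it to LEfSe and Spearman is a reading of the text. This stands. But if it does not apply, the microbiome tests have no stated threshold, and the gap remains.
- **Exploratory label.** The plan calls the correlations exploratory and the signatures potential. This lowers the weight of the point for the correlations. The label is not attached to LEfSe, although that sentence also speaks of potential differences.
- **Other analyses for Aim 3.** ANOSIM, PCoA and the diversity measures address community composition without testing taxon by taxon. A reader might infer that Aim 3 would be answered mainly by chance findings. The documents do not support that: those analyses are untouched, and nothing shows how many taxon effects are real.
- **Size.** A reader might also infer that dozens of false signatures are to be expected. That cannot be derived from the documents, which give neither a taxon count nor a closed marker list. At 0.05, 24 false correlations need 480 tests: 120 taxa with 4 markers, or 37 taxa with all 13. With 100 taxa and only the named markers, the expected count is 15 to 20.
- **Pooling.** The plan does not say that visits will be pooled. The inflated error rates in Step 4 are conditional on that choice. What is established is that the unit of analysis is unspecified.

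**Conclusion.** The point holds in a limited form. No multiplicity rule, test family or unit of analysis is specified for the taxon-level tests or the taxa-by-marker correlations. On a literal reading of the alpha sentence and an assumed 100 taxa, about 5 false taxa are expected from one pass of taxon tests under the null, before any LDA cut-off. The expected number of false correlations is 15 to 20 with the named markers and 65 with all measured ones. Across 20 to 300 taxa and 3 to 13 markers, the correlation count runs from 3 to 195, so no single figure should be quoted without its assumptions. The 12% to 27% error per test applies only if visits are pooled.

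The change should be made, because LEfSe supplies the taxon list for a numbered aim. It matters less for the correlations, which are already labelled exploratory. The LDL-C and blood pressure analyses, ANOSIM and the diversity analyses are not affected.

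**What to change.** Add to the microbiome paragraph:

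1. The taxonomic level to be tested, any prevalence filter, the LDA cut-off for LEfSe, and a closed list of markers for the correlations, so that the families of tests are defined.
2. Benjamini-Hochberg adjustment (for example at q < 0.05) across taxa within each treatment comparison, and across the taxa-by-marker family. Report q-values and the number of tests in each family.
3. Correlations computed on one within-person change per participant, for low dose minus placebo and high dose minus placebo separately, and still labelled exploratory. Keeping both doses preserves the link to the dose-response aim. Two sets of changes double the number of correlations, so state whether the family is defined per dose or over both.

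The cost is wording and a few lines of analysis code, with no new samples, visits or participants. The downside is that fewer taxa and correlations will be nominally significant.

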**BUDGET**

Period: 2/1/18 - 1/31/19

Title of Proposal: Dose Response Effects of Freeze Dried Strawberry Powder  
Supplementation on Vascular Function, Blood Markers of Cardiovascular Risk, and the Gut

Key Personnel	Rate	1st Year
[name]	1%	
Salary Requested	\$	805
Benefits (32.00%)	\$	258
[name]	100%	
Salary Requested	\$	47,660
Benefits (22.8%)	\$	10,866
Other Personnel		
TBD Research Technician	25%	
Salary Requested	\$	6,000
Benefits (32.00%)	\$	1,920
Personnel Subtotal:	\$	67,509
Equipment		
SphygmoCor System	\$	30,000
Supplies and Materials		
Lab supplies	\$	2,790
Equipment Maintenance	\$	3,500
Subject pay (200 x 50)	\$	2,000
Recruitment (advertising, etc.)	\$	750
Screening fees/services	\$	1,000
Screening Assays	\$	1,000
Fees for Collaboratory space	\$	2,667
Publication and Travel**		
Conference and Publication fees	\$	-
Endpoint Analysis		
Lipids and Lipoproteins	\$	1,000
Insulin and Glucose	\$	1,600
Inflammatory Markers	\$	-
Microbiome	\$	-
Materials, Participants, Equipment and Publication	\$	46,307
Yearly total	\$	113,816

